# PADDI Sleep Substudy: Statistical Analysis Plan

This is the second version of the SAP and was written after the data had been de-identified as regards to treatment and with further analysis added.

## General principles

The analysis and reporting of the results will follow the CONSORT guidelines. [1] Baseline characteristics will be tabulated by Dexamethasone and placebo groups using appropriate summary statistics and will include PSQI score. [2] Data for the primary endpoint will be derived from those patients enrolled into the PADDI-SLEEP substudy (those who completed the extra sleep questionnaires). Data for all endpoints will be analysed using the modified intention-to-treat (mITT) and per protocol (PP) populations, with the mITT analysis regarded as the principal analysis. Full definitions of mITT and PP are provided below.

Further sensitivity analyses will make post-hoc adjustment for any variables exhibiting substantial imbalance across treatment arms at baseline (Table 1). Interpretation of all endpoints will be based on post estimates, confidence intervals and P-values. A nominal 5% significance level will be employed.

## Null hypothesis

The intraoperative administration of intravenous dexamethasone 8 mg to patients undergoing elective non-cardiac and non-obstetric surgery, compared with placebo, is *non-inferior* to placebo in terms of postoperative sleep quality.

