## Sample size analysis

There are no published data available to use for accurate sample size estimation. We have collected data on 30 patients at Westmead Hospital that suit the PADDI inclusion criteria but who have not received dexamethasone. The mean RCSQ score on night one postoperatively was 50.17 mm, with a standard deviation of 25.28. A decrease in a patient's RCSQ score by 7.5mm (15% relative decrease) would be considered a clinically meaningful difference and hence we have chosen this as our non-inferiority margin (delta). To detect a non-inferiority margin of 15% with 90% probability (power), where non-inferiority is concluded if the upper endpoint of the two-sided 95% confidence interval for the difference in sleep quality is less than 7.5mm, requires a sample size of 195 patients per group (total 390 patients). Target recruitment set at 410 patients in total to account for 5% losses to follow up.

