## Outcomes

The primary outcome is sleep quality on night one (as assessed using the RCSQ). As the distribution of the sleep score is not normal, median regression will be undertaken to assess the difference in medians between the two treatment groups. For the sensitivity analysis, baseline characteristics will be examined and adjustment will be made for differences between the groups. The variable, preop sleep quality, is considered a major confounder and will be included in the adjusted models.

Histogram of sleep quality night one showing two peaks.

The secondary outcome is sleep quality on night two. The same analysis will be undertaken as per night one. Some people would have been discharged on day 1 but for consistency the same variables will be adjusted for as for night one in the sensitivity analysis.

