Results will be presented as a graph for night one and in table format. A graph of the estimates from the three methods will be presented (similar to a forest plot), with the non-inferiority margin ( $\Delta$ ) of -7.5 drawn in as a line.

[figure not shown]

Image as per Schumi, J., Wittes, J.T. Through the looking glass: understanding non-inferiority. *Trials* **12**, 106 (2011). <https://doi.org/10.1186/1745-6215-12-106>

Table 3: Variables of interest post randomisation.

	Dexamethasone	Control	Estimate (95% CI)	p-value
Any nausea or vomiting up to 24 hours post-surgery				
Any antiemetic up to 24 hours post-surgery				
Worst nausea rating PACU				
Anti-emetic PACU				
Anti-emetic Day 1				
Worst nausea rating Day 1				
Any vomiting PACU				
Any vomiting Day 1				
Number of vomiting events PACU				
Number of vomiting events Day 1				
Worst pain (movement) PACU				
Worst pain (rest) PACU				
Worst pain (movement) Day 1				
Worst pain (rest) Day 1				
Sleep location night 1				
Noise level (VAS score) night 1				
Sleep location night 2				
Noise level (VAS score) night 2				
Non-study DXA during surgery				
Non-study dexamethasone PACU				
Non-study dexamethasone Day 1				

Table 4: Individual components of the Quality of Sleep Questionnaire (will not test)

	Placebo	Dexamethasone
Night one		
My sleep last night was: light (0) - deep (100)		
Last night, the first time I got to sleep I: just never could not fall		

asleep (0) - fell asleep almost immediately (100)		
Last night I was: awake all night long (0) - awake very little (100)		
Last night, when I woke up or was awakened I: couldn't get back to sleep (0) - got back to sleep immediately (100)		
I would describe my sleep last night as: a bad night's sleep (0) - a good night's sleep (100)		
I would describe the noise level last night as: very noisy (0) - very quiet (100)		
Night two		
My sleep last night was: light (0) -deep (100)		
Last night, the first time I got to sleep I: just never could not fall asleep (0) - fell asleep almost immediately (100)		
Last night I was: awake all night long (0) - awake very little (100)		
Last night, when I woke up or was awakened I: couldn't get back to sleep (0) - got back to sleep immediately (100)		
I would describe my sleep last night as: a bad night's sleep (0) - a good night's sleep (100)		
I would describe the noise level last night as: very noisy (0) - very quiet (100)		

Name \_\_\_\_\_

Date \_\_\_\_\_

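### The hypothesis labelled null is non-inferiority itself, and the planned p-values are not tied to the 7.5 mm margin

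*SAP*

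**What the plan says.** The Null hypothesis section states that intraoperative dexamethasone, "compared with placebo, is *non-inferior* to placebo in terms of postoperative sleep quality". It gives no margin and no alternative hypothesis.

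General principles says: "Interpretation of all endpoints will be based on post estimates, confidence intervals and P-values". It adds: "A nominal 5% significance level will be employed". It does not say whether the level is one- or two-sided, or which value of the difference the p-value tests.

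For the primary outcome, the Outcomes section says that "median regression will be undertaken to assess the difference in medians between the two treatment groups". No margin is mentioned there. Table 2 has a p-value column beside the difference and its 95% CI, with no note on the null value.

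The margin appears in two other places. Sample size analysis justifies it ("A decrease in a patient's RCSQ score by 7.5mm (15% relative decrease) would be considered a clinically meaningful difference") and gives a success rule: "non-inferiority is concluded if the upper endpoint of the two-sided 95% confidence interval for the difference in sleep quality is less than 7.5mm". The description of the results graph, after Table 2, has the margin "of -7.5 drawn in as a line".

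**The concern.** A non-inferiority trial protects patients by making harm of at least the margin the default, so that the data must overturn it. The null is that dexamethasone is worse than placebo by 7.5 mm or more, and rejecting it supports non-inferiority. The SAP puts the claim to be shown in the null. Read literally, weak or noisy data would leave that claim standing.

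The p-values do not repair this. A regression p-value, unless otherwise specified, usually tests a difference of zero, which is not the question here. With sidedness and null value both unstated, two analysts could fill the Table 2 column differently and both claim to follow the plan. A reader who pairs a stated null of non-inferiority with a p-value above 0.05 may take the result as confirmation.

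The rule that would prevent this sits only in the sample size section, and its sign disagrees with the graph.

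**Working it through.** **Inputs.** From Sample size analysis: SD 25.28 mm, margin 7.5 mm, power 90%, 195 per group, two-sided 95% CI. A true difference of zero is assumed for the sample size, because the SAP does not state one. Below, d is dexamethasone minus placebo. Higher scores mean better sleep (item anchors in Table 4), so negative d is worse.

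**1. The plan's own figure.** n per group = 2 × SD² × (z_alpha + z_beta)² / margin² = 2 × 25.28² / 7.5² × (z_alpha + 1.2816)² = 22.723 × (z_alpha + 1.2816)².
- One-sided 2.5% (the stated 95% CI rule): 22.723 × 3.2415² = 238.8, so 239.
- One-sided 5% (a 90% CI): 22.723 × 2.9264² = 194.6, so 195.

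The stated 195 matches one-sided 5%, not the stated CI rule. That is a separate point, but it shows that the sidedness of the 5% level is not a formality in this plan.

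**2. Standard error.** SE = 25.28 × sqrt(2/195) = 2.56 mm. The 95% CI half-width is 1.96 × 2.56 = 5.02 mm.

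**3. Rule based on the 95% CI.** At true d = -7.5, the lower limit lies above -7.5 with probability 2.5%. This is the intended false-claim rate and does not depend on the SE.

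**4. Non-significance against zero taken as success.** At true d = -7.5, d/SE = -7.5/2.56 = -2.93. P(p > 0.05) = Φ(1.96 + 2.93) - Φ(-1.96 + 2.93) = 1 - Φ(0.97) = 16.6%.

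This SE is for means, while the plan analyses medians of a two-peaked score and gives no SE for that. As an assumed range, an SE 25% smaller (1.92) gives 1 - Φ(3.91 - 1.96) = 2.6%, and an SE 25% larger (3.20) gives 1 - Φ(2.34 - 1.96) = 35%. Under this misreading, less precise data make a false claim more likely.

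**5. The opposite error.** A result significantly worse than zero yet wholly inside the margin needs a CI that fits between -7.5 and 0. At the planned precision the CI is 2 × 5.02 = 10.04 mm wide, so this cannot occur. A small p-value beside a non-inferior result could arise only if dexamethasone were better.

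**6. Direction.** An upper limit below +7.5 rules out harm only if the difference is placebo minus dexamethasone. A margin line at -7.5 marks harm only if it is dexamethasone minus placebo. The SAP does not define the difference, and Table 2 does not settle it. If the upper-limit rule were applied to dexamethasone minus placebo, it would rule out a large benefit and say nothing about harm.

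**The case against.** The strongest defence is that the plan contains the right test under the wrong label. Sample size analysis gives an explicit 95% CI criterion against 7.5 mm, the graph draws the margin, and General principles lists estimates and intervals alongside p-values. Correcting the hypothesis wording changes no estimate, interval or design figure. Most of this stands, and it lowers the severity.

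It also rules out several stronger readings that a reader might infer:
- *That the plan accepts p > 0.05 as proof.* The SAP nowhere says so. The 16.6% belongs to a possible misreading, not to a stated rule.
- *That failing to reject the null as written would pass a deficit at the margin 97.5% of the time* (one-sided 2.5%; 95% at one-sided 5%). This follows from the literal wording, but no such test is planned.
- *That the 5% level contradicts the 95% CI.* A two-sided 5% level agrees with it. The fault is that sidedness is not stated.
- *That the regression p-value is fixed as a test of zero.* This is usual practice, but the SAP leaves the null value open.
- *That the 50% chance of p > 0.05 at a true 5 mm deficit is an error rate.* A 5 mm deficit lies inside the 7.5 mm margin, so concluding non-inferiority there is not a false claim.

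The defence does not explain why the decisive rule is absent from the sections that govern analysis and interpretation, why p-values are listed alongside intervals without a margin, or which sign the difference takes.

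**Conclusion.** The point holds as a should-fix. The null hypothesis is inverted, the p-values have no stated sidedness or null value, and the planned regression is not linked to the margin. The CI rule and the margin line mitigate this, but the rule is misplaced and its direction does not match the graph.

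The illustrative cost of the misreading is a false-claim rate of about 17% instead of 2.5% at a true 7.5 mm deficit. That rests on a normal approximation for a difference in means, SD 25.28 and 195 per group, and it would differ for the planned medians. The documents do not support saying that the plan would declare non-inferiority from a non-significant result.

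**What to change.** 1. Define the difference once, as dexamethasone minus placebo, and use it in every table and graph.
2. Replace the Null hypothesis text with H0: difference ≤ -7.5 mm, and H1: difference > -7.5 mm.
3. State that non-inferiority is concluded only if the lower limit of the two-sided 95% CI is above -7.5 mm. Reword the rule in Sample size analysis to match, so that it agrees with the line on the graph.
4. Repeat this rule in the Outcomes section, and refer to it in General principles, as the sole basis for the primary conclusion.
5. In Table 2, report the one-sided p-value against -7.5 mm, judged at 2.5%. With a normal approximation this is the upper tail of (estimate + 7.5)/SE. If the CI is built another way, the CI governs. Label any zero-difference p-value as superiority or inferiority information only.

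The cost is revised wording in four short places (Null hypothesis, General principles, Sample size analysis, Outcomes) and a Table 2 column header. It needs no new data. The mismatch between 195 per group and the 95% CI rule remains to be dealt with separately.

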## Primary outcome

Patient self-assessed sleep quality measured on postoperative night one.

## Secondary outcome

Patient self-assessed sleep quality measured on postoperative night two.

## Sample size analysis

There are no published data available to use for accurate sample size estimation. We have collected data on 30 patients at Westmead Hospital that suit the PADDI inclusion criteria but who have not received dexamethasone. The mean RCSQ score on night one postoperatively was 50.17 mm, with a standard deviation of 25.28. A decrease in a patient's RCSQ score by 7.5mm (15% relative decrease) would be considered a clinically meaningful difference and hence we have chosen this as our non-inferiority margin (delta). To detect a non-inferiority margin of 15% with 90% probability (power), where non-inferiority is concluded if the upper endpoint of the two-sided 95% confidence interval for the difference in sleep quality is less than 7.5mm, requires a sample size of 195 patients per group (total 390 patients). Target recruitment set at 410 patients in total to account for 5% losses to follow up.

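### The 195 per group matches a one-sided 5% test (90% CI); under the SAP's own two-sided 95% CI rule the stated 90% power is about 83%

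*SAP*

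**What the plan says.** All the inputs stand in the SAP section Sample size analysis.

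- **Pilot data** (30 patients at one hospital, no dexamethasone): "The mean RCSQ score on night one postoperatively was 50.17 mm, with a standard deviation of 25.28".
- **Margin:** "A decrease in a patient's RCSQ score by 7.5mm (15% relative decrease) would be considered a clinically meaningful difference", and this is adopted as the non-inferiority margin.
- **Power:** "To detect a non-inferiority margin of 15% with 90% probability (power").
- **Decision rule:** "non-inferiority is concluded if the upper endpoint of the two-sided 95% confidence interval for the difference in sleep quality is less than 7.5mm".
- **Result:** this "requires a sample size of 195 patients per group (total 390 patients").
- **Losses:** "Target recruitment set at 410 patients in total to account for 5% losses to follow up".

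On the error rate, the section General principles adds only that "A nominal 5% significance level will be employed", without saying whether it is one- or two-sided. Table 2 also plans a 95% interval for the difference. The SAP nowhere mentions a 90% interval, a one-sided 5% test, or an expected true difference other than zero.

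**The concern.** A non-inferiority conclusion uses only one limit of the interval. With a two-sided 95% interval, the test against the margin is therefore one-sided at 2.5%, and the sample size formula needs the normal quantile 1.960. The stated sample size looks as if 1.645 was used, which belongs to a one-sided 5% test or a 90% interval. The rule and the sample size would then describe two different tests.

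Two things are at stake.

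- In a non-inferiority trial, the planned power shapes how an inconclusive result is read. A reader told 90% would give such a result more weight against the drug than the design justifies.
- The mismatch leaves room to argue later that a 90% interval was intended all along. That question should not be open once results are known.

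**Working it through.** **Inputs.** SD σ = 25.28 mm, margin Δ = 7.5 mm, power 90% and equal groups, all from Sample size analysis. The true difference is taken as 0. This is an assumption: the SAP states no value, and zero is the usual default.

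**Formula for a comparison of means (normal approximation).** n per group = 2 (z_α + z_0.90)² σ² / Δ².

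The part that does not depend on α is 2 × 25.28² / 7.5² = 1278.16 / 56.25 = 22.723. The power quantile is z_0.90 = 1.2816.

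**Reproducing the SAP's figure (one-sided 5%).** (1.6449 + 1.2816)² = 8.564, and 8.564 × 22.723 = 194.6, rounded up to **195**. This matches exactly.

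**Applying the SAP's own rule (two-sided 95% interval, one-sided 2.5%).** (1.9600 + 1.2816)² = 10.507, and 10.507 × 22.723 = 238.8, rounded up to **239** per group, 478 in total. The stated 195 is 44 per group short, or 18%.

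**Power at the stated size.** SE = 25.28 × √(2/195) = 2.560 mm. Power = Φ(7.5/2.560 − 1.960) = Φ(0.970) = **83.4%**. The noncentral t distribution gives 83.2%. With 1.645 in place of 1.960 the same calculation gives 90.05%, which is the power the SAP claims.

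**Other readings that might explain 195:**

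| Variant | n per group |
|---|---|
| One-sided 2.5%, 90% power, noncentral t | 240 |
| One-sided 2.5%, 90% power, margin 15% × 50.17 = 7.53 mm | 238 |
| One-sided 2.5%, 80% power | 179 |
| One-sided 5%, 80% power | 141 |
| Two-sided equivalence, 90% power (5% or 2.5% per side) | 246 or 296 |
| One-sided 5%, 90% power | 195 |

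Only the last row gives the stated figure with the stated margin.

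**What would make 195 correct at one-sided 2.5% and 90% power.** Any one of these would do: an SD of about 22.8 mm, a margin of (1.9600 + 1.2816) × 2.560 = 8.3 mm, or a true benefit of dexamethasone of 8.3 − 7.5 = 0.8 mm. The SAP states none of them.

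**Whether the allowance for losses covers the gap.** If all 410 recruits were analysed (205 per group), SE = 25.28 × √(2/205) = 2.497 and power = Φ(7.5/2.497 − 1.960) = 85.2%. That is still below 90%, and the SAP reserves those extra patients for losses.

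**The case against.** The strongest reply accepts the arithmetic and questions its weight.

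- **The error no longer changes anything.** The opening of the SAP says this second version was written once the data were held in de-identified form, and the Outcomes section already describes the shape of the night-one scores. The sample is fixed. The estimator, interval, margin and populations are unaffected, and the 95% rule is the stricter one. The interval reported will itself show the precision achieved. This is right, and it limits the matter to a false statement of power; the final inference remains valid. The SAP still asserts the figure, however, and a trial report would be expected to repeat it.
- **83% is not the power of the planned test.** The Outcomes section specifies median regression on a two-peaked score, whereas the calculation concerns means. For illustration, if the scores were normal with SD 25.28, the SE of a difference in medians would be about 2.560 × √(π/2) = 3.209 mm, and power would be Φ(7.5/3.209 − 1.960), about 65%. With two peaks it could be higher or lower. This stands as a caveat. It gives no support to the 90%.
- **The SD is uncertain.** It rests on 30 patients. Under normality its 95% interval is about 20.1 to 34.0 mm, which puts power at 195 per group anywhere from about 96% to 59%. This also stands, but it applies equally to the SAP's own figure. The inconsistency lies in what follows from the stated SD.
- **The 5% level might have been meant as one-sided.** General principles leaves this open, but Sample size analysis does not: it names a two-sided 95% interval.

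**Conclusion.** The concern holds. On the SAP's own inputs and decision rule, 195 per group gives about 83% power, not 90%, and the type II error is about 17%, not 10%. For 90%, 239 per group would have to be analysed. The exact match at one-sided 5% makes the use of 1.645 in place of 1.960 the likely source.

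These figures rest on a comparison of means, the normal approximation, SD 25.28 mm, margin 7.5 mm and a true difference of zero. They correct the SAP's calculation as it is set out and do not describe the power of the median regression. The one-sided type I error stays at 2.5% as long as the 95% interval is used.

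**What to change.** Keep the two-sided 95% interval as the decision rule and replace the power claim in Sample size analysis with a sentence such as:

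> With 195 patients per group, the power to conclude non-inferiority is about 83%, for a difference in means with SD 25.28 mm, margin 7.5 mm, true difference 0 and a two-sided 95% confidence interval (one-sided alpha 0.025).

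A short note that this figure does not cover the median regression in the Outcomes section would be a useful addition.

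Do not reconcile the two by moving to a 90% interval. That would relax the success criterion in a plan revised after data collection.

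The cost is one sentence and a less favourable stated power. No extra patients are needed. Restoring 90% by recruitment would instead have taken 478 analysed patients, or 478 / 0.95 = 503.2, that is 504 recruited, against the target of 410.

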## Statistical Analyses

### A. Modified ITT (mITT) population

The mITT population will consist of all randomised patients who undergo induction of anaesthesia and eligible surgery (surgery with a total surgical incision length >5 cms; this is an arbitrary incision length, chosen by using a Delphi approach among the members of the trial steering committee). The mITT patients will be analysed according to the group to which they were randomised, whether they receive study drug or not, or whether they receive additional (non-study) glucocorticoid or not.

The only exclusions will be for:

- a) patients who do not undergo surgery under general anaesthesia on the scheduled date
- b) patients who withdrew consent prior to surgery
- c) clinician refusal at the time of surgery
- d) duplicate randomisation
- e) study drug not available at the time of surgery
- f) screening failures

Patients whose consent is withdrawn post-operatively will have their data used up until the time of withdrawal.

### B. Per Protocol (PP) population

[figure not shown]
The PP population will comprise those patients who completed the treatment to which they were originally allocated, meaning ONLY those patients who receive a single dose of study drug or placebo according to their original randomised allocation. This analysis specifically excludes patients who were not given their randomised study drug at the commencement of surgery **AND** patients who received their study drug but also receive non-study glucocorticoid within the 24 hours following surgery. This also excludes patients randomised to dexamethasone whose randomisation was overridden and received open-label dexamethasone within the 24 hours following surgery. Patients who withdraw consent will have their data used up until the time of withdrawal.

The primary analyses will be in the mITT population, per protocol (PP) populations and a sensitivity analyses will make post-hoc adjustment for any variables exhibiting substantial imbalance across treatment arms at baseline. The mITT analysis will be undertaken as per the main Statistical Analysis Plan for the PADDI trial. The per protocol analysis will only exclude those who did not get the study drug or those who got non-study dexamethasone during surgery or in PACU, that is they received non-study dexamethasone prior to the primary outcome occurrence. Because the patients not meeting the PP population definition have been excluded, there may no longer be balance in patient characteristics between dexamethasone and placebo arms. The baseline and pre-operative characteristics in the dexamethasone and

placebo arms will be tabulated and compared for the 'compliant' (PP) patients. Any variables exhibiting imbalance will be adjusted for.

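### The SAP defines the per-protocol population in two incompatible ways, and neither time window matches the stated reason for excluding patients

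*SAP*

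**What the plan says.** **First paragraph of section B.** The per-protocol (PP) set holds "ONLY those patients who receive a single dose of study drug or placebo according to their original randomised allocation". It leaves out patients not given their study drug at the start of surgery, and "patients who received their study drug but also receive non-study glucocorticoid within the 24 hours following surgery". A further sentence removes patients allocated to dexamethasone whose allocation was overridden with open-label drug.

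**Second paragraph of section B.** The PP analysis "will only exclude those who did not get the study drug or those who got non-study dexamethasone during surgery or in PACU". The reason follows: "that is they received non-study dexamethasone prior to the primary outcome occurrence".

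**Rank of the populations.** General principles has all endpoints analysed in both populations, "with the mITT analysis regarded as the principal analysis". Section B opens its second paragraph with "The primary analyses will be in the mITT population, per protocol (PP) populations".

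**Related text.** Section A keeps mITT patients in their randomised arm whatever additional glucocorticoid they receive. The list of postoperative variables and Table 3 record non-study dexamethasone for three periods: during surgery, in PACU, and on day 1.

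**The concern.** The trial aims to show that dexamethasone does not worsen sleep by more than 7.5 mm. The mITT set keeps placebo patients who were given a glucocorticoid anyway. If the drug does harm sleep, such use pulls the arms together and favours a non-inferiority conclusion. The SAP does not say this, but it is the usual reason for placing a PP analysis beside the mITT analysis. The check serves its purpose only if everyone knows in advance who is in the PP set.

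Here two analysts who follow the SAP could build different PP sets for the primary outcome, and each could cite a paragraph in support. The SAP describes itself as a second version, written when the data were already in hand without treatment labels. A choice still open at that stage should be closed before the labels are restored.

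**Working it through.** The main check is a comparison of texts. Rule 1 is the first paragraph of section B and rule 2 the second. The word *only* in rule 2 makes its list closed, so the rules cannot be merged by applying both sets of exclusions.

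Each patient below received the allocated study drug, except in the last row.

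| Patient | Rule 1 | Rule 2 | Exposure before night one? |
|---|---|---|---|
| Non-study dexamethasone in PACU | out | out | yes |
| Non-study dexamethasone on the ward, evening of surgery | out | in | yes |
| Another glucocorticoid on the ward, evening of surgery | out | in | yes |
| Non-study dexamethasone next morning, still inside 24 hours | out | in | no |
| Non-study dexamethasone during surgery | unclear | out | yes |
| Study drug not given | out | out | not applicable |

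1. The rules disagree outright in rows two to four.
2. Row five is unclear under rule 1. Its window begins after surgery, but its single-dose requirement may be meant to cover use during surgery. The finding does not rest on this row.
3. Rule 2 fails its own reason in row two. A ward dose that evening also precedes the primary outcome, yet the patient is kept. Row three is the same for other agents.
4. Rule 1 fails in row four. It can remove a patient for something that happened after the primary outcome.
5. Row two is a case the SAP provides for, since it plans to tabulate dexamethasone use after PACU under day 1.

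**Size.** Two inputs are needed: how often non-study steroid is used in each arm, and what share of patients the rules classify differently. The SAP gives neither.

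**Power if both populations had to show non-inferiority.** This matters only for the optional suggestion under the fix. Inputs from the SAP's sample size section: SD 25.28 mm, margin 7.5 mm, 195 per group, 90% power, two-sided 95% interval.

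- Plan's own figure: n per group = 2 × (z for alpha + z for power)² × SD² / margin². With 1.960 and 1.282 this gives 239. With 1.645 and 1.282 it gives the stated 195. So 195 matches a two-sided 90% interval, which is a separate matter.
- Power under the stated 95% interval = Φ(7.5/SE − 1.96), with SE = 25.28 × √(2/n).
- n = 195: SE = 2.56, power 83.4%.
- PP set assumed to lose 10% (n = 175.5): SE = 2.70, power 79.4%.
- PP set assumed to lose 20% (n = 156): SE = 2.86, power 74.5%.

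The 10% and 20% are assumptions. The formula is for means under normal theory, while the SAP plans median regression on a two-peaked score, so the figures are a guide only.

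**The case against.** **The second paragraph may be the operative rule.** It can be read as the specific rule for this substudy, following a general definition, because it refers to the primary outcome. That is a fair reading, but the SAP does not say that one paragraph replaces the other. Even if rule 2 governs, its window does not match its reason.

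**The single-dose wording may cover steroid use during surgery.** This stands, which is why that case is treated as unclear.

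**Rank of mITT and PP.** A reader might infer that the SAP contradicts itself on whether PP is a primary analysis. The text does not support so strong a reading. General principles plainly ranks mITT first. The section B sentence, "The primary analyses will be in the mITT population, per protocol (PP) populations and a sensitivity analyses", also takes in the sensitivity analysis, and Table 2's title groups the same three methods under the primary outcome. The natural meaning is analyses of the primary outcome. What remains is loose wording.

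**Error rates.** A reader might calculate how steroid use in the placebo arm raises the chance of a false non-inferiority conclusion in mITT and offer that as the size of this defect. It measures something else: no PP wording changes the mITT result.

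**Choice driven by results.** A reader might suspect that the PP set was chosen to suit the findings. Data without treatment labels do not show which set favours which conclusion. The risk arises only if the choice stays open after unblinding.

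**Conclusion.** The contradiction holds on the text alone and needs no assumption. The two PP rules differ in agent and window, the same patient can be in one set and out of the other, and neither window fits exposure before night one. The PP definition is wrong as written and has to be reconciled.

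The effect on the results cannot be sized from the SAP, and no figure is claimed. It could be negligible if few patients received non-study steroid outside surgery and PACU. The mITT analysis, which the SAP names as principal, is not affected. Nor does the SAP's failure to require non-inferiority in both populations count as an error here, since it has named its principal analysis.

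**What to change.** Before unblinding:

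1. Keep one PP definition and delete the other. For night one, exclude patients not given their allocated study drug and patients given non-study glucocorticoid from induction to the end of night one.
2. If agents or times were not recorded that finely, use the closest window the collected data allow and say so. The SAP lists only non-study dexamethasone, for surgery, PACU and day 1. It does not show that other agents, or timing within day 1, can be separated.
3. State which PP set applies to night two. The listed records stop at day 1, so a window running to night two may not be feasible.
4. Reword the section B sentence on primary analyses to agree with General principles: mITT principal, PP supporting.

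Optional: require non-inferiority in both mITT and PP. This would be a new decision rule, not a correction. On the figures above, power in the PP set alone would be 79.4% or 74.5% if it lost 10% or 20% of patients, against 83.4% at full size, and power to succeed in both sets cannot exceed that of the PP set.

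The cost of items 1 and 4 is a few sentences, because both analyses are already planned. Items 2 and 3 need a check of what was recorded. If treatment labels have already been restored, results under both PP rules should be reported.
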